#### 7.6.2 Dose modifications

*The dose modification guidelines are intended to be applied when the investigator determines the events related to Tenalisib.*

**Table 3: Dose Modifications for Hematologic Toxicity**

Worst CTCAE Grade Toxicity	Action to be Taken
HEMATOLOGIC	
Neutropenia (ANC)	
Grade 3 $1.0 \times 10^9/\text{L} < \text{ANC} \leq 0.5 \times 10^9/\text{L}$	Maintain dose level. Monitor ANC at least weekly.
Grade 4 $0.5 \times 10^9/\text{L} < \text{ANC}$	First incidence: Hold* dose until resolved to $\leq$ Grade 2 or baseline, Restart Tenalisib at 400 mg BID dose level. Subsequent occurrence: Hold dose until resolved to $\leq$ Grade 2 or baseline, consider growth factor support. Discontinue if further dose modification required.

Grade 3 Febrile neutropenia ANC <1000/mm  with a single temperature of > 38.3 0C (101 0F) or a sustained temperature of ≥ 38 0C (100.4 0F) for more than one hour.	Hold* dose until resolved to ≤ Grade 2 or baseline, consider growth factor support, then reduce by 1 dose level.
Thrombocytopenia	
Grade 3 (50.0 X 10  /L < PLT ≥ 25.0 X 10  /L)	Maintain dose level. Monitor platelet count at least weekly.
Grade 4 25.0 X 10  /L < PLT	1st occurrence: Hold** dose until resolved to ≤ Grade 2 or baseline, Restart Tenalisib at 400 mg BID dose level. Subsequent Occurrences: Hold dose until to ≤ Grade 2 or baseline, consider platelet transfusion as necessary. Discontinue if further dose modification required. Note: If the count is <50 X 10  /L before initiation of therapy (e.g. in case of marrow involvement), the dose reduction should be done as per investigator's judgement.

\*If study drug is delayed >2 weeks because of an adverse event, treatment strategy should be discussed with medical monitor.

\*\* Patient receiving concomitant medication (e.g. anticoagulants, anti-platelets, aspirin, or low molecular weight heparin) must be discussed with the medical monitor for continued management.

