### **3.5.5 Precautions and risks associated with Investigational Products**

- Monitoring of liver enzymes and levels of TSH, T3, and T4 in subjects receiving Tenalisib is recommended based on target organ toxicity. Patients should be monitored for increased ALT/AST, skin rash, neutropenia as these events are reported with Tenalisib. Monitor patients for signs and symptoms of these events and interrupt

Tenalisib for Grade 3 or higher event. In addition, enteritis (colitis), pneumonia/pneumonitis as these events are reported with other PI3K inhibitors.

- Tenalisib may cause serious infections that may include sepsis and other infections. Monitor patients for signs and symptoms of infection and interrupt Tenalisib for Grade 3 or higher infection.
- Tenalisib elicits no photo instability upon exposure to ultraviolet (UV) radiations. However, in absence of in vitro data, possibility of photo-toxicity with Tenalisib cannot be ruled out.
- Tenalisib demonstrated moderate to high inhibition of CYP3A4 enzymes. Therefore, concomitant administration of Tenalisib with CYP3A4 substrates (e.g. calcium channel blockers, warfarin, carbamazepine, macrolide antibiotics, lovastatin, simvastatin, terfenadine) may reduce clearance of these drugs increasing the risk of adverse events. Similarly, as Tenalisib is inhibited by CYP3A4/5 and CYP2C9, there is possibility of drug interaction with inhibitors or inducers of CYP3A4 and CYP2C9. If concomitant treatment of these drugs are clinically warranted, careful observation of the patient is advised. Raised INR has been reported with concomitant warfarin administration. Therefore, use of heparin or warfarin is generally avoided. Low molecular weight heparin (LMWH) is advised for prophylaxis and treatment of venous thrombosis.
- Strong inhibitor or inducers should be avoided as directed in Section on prohibited medication. Please refer to the recent Investigator Brochure for additional safety information.
- In absence of reproductive toxicity and genotoxicity data, the study participants should be advised to follow post treatment contraceptive measures.

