**Table 4: Dose Modifications for Non-Hematologic Toxicities**

NON-HEMATOLOGIC	Action to be Taken
Renal*	If serum creatinine Grade ≥3 (>3 x baseline or >3 x ULN), hold dose until ≤ grade 2. Monitor serum creatinine at least twice a week until resolution to ≤ grade 2, and then at least one week until it resolves to ≤ grade 1.
Hepatic*	
Transaminitis
 
Grade ≥ 1 Transaminitis (ALT/AST > 1-3 X ULN):
 
 
• Maintain Tenalisib dose and initiate prednisone 40 mg daily.
 
• Monitor AST/ALT weekly until resolved.
 
• Withhold Tenalisib in case of development of grade 2 transaminitis or worsening of Grade 1 transaminitis while on steroids.
 
 
Grade ≥ 3 Transaminitis (ALT/AST >5–20 X ULN):
 
 
• Withhold Tenalisib and monitor ALT/AST twice a weekly until Grade ≤1; restart Tenalisib at 400 mg BID dose level.
 
• Initiate prednisone 1 mg/kg in case no improvement with discontinuation of Tenalisib in 1 week.
 
• Monitor ALT/AST twice a weekly until Grade ≤1; restart Tenalisib at 400 mg BID dose level and taper steroid.
 
• If no immediate response to steroids within 7 days, initiate mycophenolate mofetil.
 
• In case of recurrence of transaminitis at reduced doses, discontinue Tenalisib permanently after assessing risk versus benefit.
 
 
Grade ≥ 4 Transaminitis (ALT/AST >20 X ULN):
 
 
• Tenalisib should be permanently discontinued.
 

	
Bilirubin:
 
 
• Grade <math>\geq 2</math> (<math>> 1.5-3 \times \text{ULN}</math>): Maintain Tenalisib dose. Monitor at least weekly until <math>\leq 1 \times \text{ULN}</math>
 
• Grade <math>\geq 3</math> (<math>> 3-10 \times \text{ULN}</math>): Withhold Tenalisib. Monitor at least weekly until bilirubin is <math>\leq 1 \times \text{ULN}</math>; restart Tenalisib at 400 mg BID dose level.
 
• Grade <math>\geq 4</math> (<math>> 10 \times \text{ULN}</math>): Discontinue Tenalisib permanently
 

Infection	
Grade 3 or higher sepsis or pneumonia
 
 
• Interrupt Tenalisib until infection has resolved.
 

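### For a Tenalisib-related, non-febrile Grade 3 neutropenia, Protocol Section 3.5.5 says to interrupt dosing and Table 3 says to maintain it, and nothing says which governs

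*Protocol*

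**What the plan says.** **Neutropenia.** Protocol Section 3.5.5 (precautions and risks) states: "Patients should be monitored for increased ALT/AST, skin rash, neutropenia as these events are reported with Tenalisib". The next sentence gives the action: "Monitor patients for signs and symptoms of these events and interrupt" "Tenalisib for Grade 3 or higher event" (one sentence, split by a page break). Table 3 in Section 7.6.2 gives the action for Grade 3 neutropenia as "Maintain dose level. Monitor ANC at least weekly". It holds the drug only at Grade 4 or for Grade 3 febrile neutropenia.

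**Infection.** Section 3.5.5 says: "Monitor patients for signs and symptoms of infection and interrupt Tenalisib for Grade 3 or higher infection". The infection row of Table 4 is limited to Grade 3 or higher sepsis or pneumonia and says: "Interrupt Tenalisib until infection has resolved". It gives no restart dose. Other Grade 3/4 non-hematologic events fall to the last row of Table 4, which at first occurrence holds the drug until Grade 2 or lower and restarts at 400 mg BID. The opening of Section 7.6 also has a general rule that allows resumption at Grade 2 or lower, or at baseline.

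**Scope.** Section 7.6.2 limits the tables to related events: "The dose modification guidelines are intended to be applied when the investigator determines the events related to Tenalisib". Section 3.5.5 carries no such limit. A note in Section 7.6 leaves dose reduction to the investigator when a cytopenia is attributed to the lymphoma.

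**Reporting.** The SAP tabulates patients with dose reductions or interruptions (Section 10.1) and TEAEs that lead to dose interruptions (Section 10.6.2). The notes to SAP Section 5.1 say that the study has been closed and Part 2 will not be performed.

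**The concern.** Neutropenia is a known toxicity of this drug. Section 1.1.2 lists it among treatment-related Grade 3 or higher events in both earlier patient studies. Inclusion criterion 7b admits patients with an ANC of 1 x 10^9/L, which is also the higher of the two figures printed in Table 3's Grade 3 row, so some patients may start close to the grade in question.

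A site that meets this event finds one section telling it to stop the drug and another telling it to continue. That is first a defect in a safety instruction. It is also a reporting problem. Safety and tolerability form the secondary objective, and an interruption count is read as a measure of tolerability. If two sites treat the same laboratory value in opposite ways, each with protocol support, the count for that event reflects partly which section was followed.

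**Working it through.** **Step 1. Compare the instructions by event, using the grade labels only.**

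| Event | Section 3.5.5 | Tables 3 and 4 (related events) | Result |
|---|---|---|---|
| Grade 3 neutropenia, non-febrile | Interrupt | Maintain, monitor weekly | Opposite |
| Grade 3 febrile neutropenia | Interrupt | Hold | Agree on stopping |
| Grade 4 neutropenia | Interrupt | Hold | Agree on stopping |
| Grade 3 ALT/AST increase | Interrupt | Withhold | Agree on stopping |
| Grade 3 rash | Interrupt | Hold (last row of Table 4) | Agree on stopping |
| Grade 3 or higher sepsis or pneumonia | Interrupt | Interrupt until resolved, no restart dose | Agree on stopping |
| Other Grade 3/4 infection | Interrupt | Hold to Grade 2 or lower, restart at 400 mg BID | Agree on stopping; recovery and restart terms differ from the sepsis/pneumonia row |

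Only the first row is a contradiction on whether to keep dosing. The ANC limits printed for Grade 3 in Table 3 describe an empty range (above 1.0 and at most 0.5). That may come from reading the PDF, and the comparison does not depend on it.

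**Step 2. Look for a rule that settles it.** Section 3.5.5 does not refer to Section 7.6, and Section 7.6 does not refer to 3.5.5. Section 3.5.5 does point to the section on prohibited medication for strong inhibitors and inducers, so cross-reference is used there, but not for toxicity. The relatedness limit and the note on disease-related cytopenia reduce the number of patients to whom Table 3 applies. They leave the related Grade 3 case contradicted.

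**Step 3. Size.** Input: in the T-cell lymphoma study (Section 1.1.2), treatment-related Grade 3 or higher neutropenia has n = 3 among 49 patients.

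- Rate: 3/49 = 6.1%.
- Exact (Clopper-Pearson) 95% limits: lower = 2.5th percentile of Beta(3, 47) = 1.3%; upper = 97.5th percentile of Beta(4, 46) = 16.9%.
- Expected among 20 patients: 20 x 3/49 = 1.2; over the interval, 20 x 0.0128 = 0.3 to 20 x 0.1687 = 3.4.

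The three events are Grade 3 or higher, and the protocol does not split them. Any Grade 4 or febrile case drops out of the conflict, so at a given rate the figure is a ceiling and the true number may be zero. The 49 also include 8 patients at 200 or 400 mg BID and 6 treated fed. If all three events fell among the 35 treated fasting at 800 mg BID, the rate would be 3/35 = 8.6%, or 1.7 of 20, still inside the range above.

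**Step 4. Which outputs move.** The interruption counts in SAP 10.1 and 10.6.2 change with the site's choice. Exposure in SAP 10.6.1 is last dosing day minus first dosing day plus 1, so a temporary interruption between those days is not subtracted.

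**The case against.** The strongest reply is that Section 3.5.5 is a general precautions paragraph with one sentence for three events, while Section 7.6 is the dose modification section, set out by event and grade. A site looking for a dosing action would naturally turn to the specific table. This makes it less likely that sites in fact diverged. But the documents do not state that reading, and Section 3.5.5 is not vague: it names the event, the grade and the action.

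It is also fair to say that the effect on analysis is small. SAP 9.1 has no formal hypotheses, safety is descriptive, and perhaps one patient's entry is at stake. That stands, and it limits the consequence for the results without touching the defect in the instruction.

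Three stronger readings are tempting and should not be drawn:

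- **That infection management is reversed in the same way.** It is not. Every text that covers a Grade 3 infection stops dosing. The differences concern which infections are covered, when dosing may resume and at what dose.
- **That about 1 in 20 patients certainly meets opposite orders.** The 3 of 49 include an unknown number of Grade 4 or febrile cases, where the texts agree on stopping.
- **That patients would move in or out of the per-protocol set.** Protocol 11.2 defines a deviation as an unintended or unanticipated departure, which following an approved dose table may not be. The examples of major deviations in SAP 7.2, though not exhaustive, concern consent and eligibility. Under SAP Section 11 the medical monitor decides PP membership. The primary efficacy set is mITT in any case. An effect is possible but not shown.

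**Conclusion.** The point holds for one defined event. On a Tenalisib-related, non-febrile Grade 3 neutropenia the protocol gives two opposite instructions and no rule of precedence, so it is wrong as written. The infection texts are a secondary inconsistency of scope, recovery threshold and restart dose. The missing relatedness condition in Section 3.5.5 is a further difference in scope.

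The expected number affected is at most about 1 of 20 (0.3 to 3.4 over the exact interval), possibly none. This assumes that the treatment-related rate in T-cell lymphoma, over mixed doses and food conditions, carries over to indolent lymphoma. The contradiction itself rests on no assumption about rates. Closure of the study does not remove the error, but it changes what can usefully be done about it.

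**What to change.** **Protocol.** Reconcile Section 3.5.5 with Table 3 on Grade 3 neutropenia and with Table 4 on infection, so that each event and grade has one action, one recovery threshold and one restart instruction. This can be done by replacing the action wording in 3.5.5 with a cross-reference to Section 7.6 once the content is agreed, or by stating which section governs. Say whether the relatedness condition of Section 7.6.2 also applies to 3.5.5, and check the printed ANC limits in Table 3 against the source file. Which action stands is for the sponsor's clinicians.

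**Study report.** Because dosing already given cannot be changed, state which rule sites followed for Grade 3 neutropenia. List any such patients with the action taken, and say how each was counted under interruptions and protocol deviations.

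**Cost.** A wording clarification and a short paragraph with a listing in the report. It needs no new patients, visits or data collection, provided the action taken for each event was recorded.

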### 7.6 Dose Modifications

All dose modifications are graded by the CTCAE v5.0.

**Note:** *If cytopenia events are deemed related to the underlying disease rather than Tenalisib, dose reduction will be done as per the investigator’s discretion.*

Patients may resume Tenalisib, provided that the toxicity has resolved to Grade  $\leq 2$  or baseline. If study drug is delayed  $> 2$  weeks because of an adverse event, re-initiation of treatment need to be discussed with the medical monitor.

At the discretion of the Investigator, a dose re-escalation may be permitted for patients who previously had a dose reduction. Holidays from study drug are discouraged. Any patient in whom similar toxicity recurs at the reduced dose should be discontinued from further Tenalisib treatment. Note: In exceptional case, a patient may be allowed following a careful assessment of benefit and risk by the investigator and with approval from the medical monitor.

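### Table 3 of the protocol prints all four neutrophil and platelet ranges with the leading inequality reversed, and its Grade 3 neutropenia action contradicts Section 3.5.5

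*Protocol*

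**What the plan says.** Table 3 is headed "Worst CTCAE Grade Toxicity" and gives a grade label, a count range and an action for each row. All counts below are in ×10⁹/L.

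- Grade 3 neutropenia: the range is printed as above 1.0 and at most 0.5. The action is "Maintain dose level. Monitor ANC at least weekly".
- Grade 4 neutropenia: the range is printed as ANC above 0.5. At first occurrence the drug is held until recovery and restarted at 400 mg BID.
- Grade 3 thrombocytopenia: "50.0 X 10 9 /L < PLT ≥ 25.0 X 10 9 /L". The dose is kept and platelets are checked at least weekly.
- Grade 4 thrombocytopenia: "25.0 X 10 9 /L < PLT". The action is a hold and a restart at 400 mg BID.

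Two other entries in the same table point the right way. The febrile row reads "Grade 3 Febrile neutropenia ANC <1000/mm" (per mm³), and the note on low pre-treatment platelets treats counts below 50 as the abnormal side. Section 7.6 adds: "All dose modifications are graded by the CTCAE v5.0".

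Section 3.5.5 names raised ALT/AST, skin rash and neutropenia as events to watch for, and tells sites to interrupt Tenalisib when one of them reaches Grade 3 or above.

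**The concern.** Lower counts are worse, so a Grade 4 row should capture the lowest counts and a Grade 3 row the band just above them. As printed, the Grade 4 rows capture everything above their cut-point and exclude the counts they exist for. No other section prints these ranges correctly, so a site that checks a laboratory value against Table 3 has no second statement of the numbers to fall back on.

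These are operative triggers for individual patients: they decide whether the drug is held and whether the dose is halved from 800 to 400 mg BID. A literal reading would hold the drug where Table 3 means it to continue, and would give no Table 3 instruction where counts are lowest.

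There is a second problem that correct grading does not remove. For a patient properly graded as having Grade 3 neutropenia, 3.5.5 and Table 3 give opposite instructions.

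**Working it through.** The plan states no derived figure here, so the check is a logical one. All counts are in ×10⁹/L.

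**Inputs.** The four ranges, the febrile row and the platelet note come from Table 3. Entry minima come from Protocol 4.1: ANC at least 1.0 (7b); platelets at least 50, or 30 with marrow involvement (7c). The grade-based interruption comes from 3.5.5.

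**Step 1: reduce each printed range.**
- Grade 3 ANC: ANC > 1.0 and ANC ≤ 0.5. No value satisfies both.
- Grade 4 ANC: ANC > 0.5.
- Grade 3 platelets: PLT > 50 and PLT ≥ 25, which is PLT > 50.
- Grade 4 platelets: PLT > 25.

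**Step 2: set the intended ranges.** Keep the table's own cut-points and make a lower count the worse grade. The febrile row (ANC below 1000/mm³, that is 1.0) and the note (platelets below 50) confirm the direction and the upper limits. The printed ≥ 25 puts the boundary value in Grade 3 for platelets; I assume the same for ANC at 0.5. This gives 0.5 ≤ ANC < 1.0, ANC < 0.5, 25 ≤ PLT < 50 and PLT < 25.

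**Step 3: compare.**

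| Count | Row met as printed | Row intended |
|---|---|---|
| ANC below 0.5 (0.1, 0.3, 0.49) | neither | Grade 4 |
| ANC 0.5 | neither | Grade 3 |
| ANC 0.51–0.99 | Grade 4 | Grade 3 |
| ANC 1.0 and above (1.2, 1.5, 4.0) | Grade 4 | neither |
| PLT below 25 (5, 10, 24) | neither | Grade 4 |
| PLT 25 | neither | Grade 3 |
| PLT 26–49 | Grade 4 | Grade 3 |
| PLT 50 | Grade 4 | neither |
| PLT 51 and above (75, 150, 250) | Grade 3 and Grade 4 | neither |

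No line matches. Under the corrected ranges every tested value falls in at most one row.

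**Step 4: patients at entry.** The lowest eligible ANC is 1.0, which exceeds 0.5. The lowest eligible platelet counts are 50 and 30, and both exceed 25. Every eligible patient therefore meets both printed Grade 4 rows before the first dose.

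**Step 5: dependence on one symbol.** The text was machine-read from PDF, and the second sign in the Grade 3 ANC row appears as ≤. If the page in fact shows ≥, that row becomes ANC > 1.0 instead of empty. ANC 0.51–0.99 would still meet only the Grade 4 row, and ANC of 0.5 or less would still meet neither.

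**Step 6: which instruction is left.**

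| Toxicity | Section 3.5.5 | Table 3, intended | Table 3, read by number |
|---|---|---|---|
| Grade 3 ANC | interrupt | maintain | hold, restart at 400 mg BID (0.51–0.99) |
| Grade 4 ANC | interrupt | hold, restart at 400 mg BID | no graded row; febrile row if febrile |
| Grade 3 platelets | silent | maintain | hold, restart at 400 mg BID (26–49) |
| Grade 4 platelets | silent | hold, restart at 400 mg BID | no graded row |

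For Grade 4 neutropenia, interruption survives through 3.5.5. What is lost is Table 3's detail on restart and dose reduction. For Grade 4 thrombocytopenia the hold itself is lost. The first line shows the 3.5.5 conflict, which remains once the signs are corrected.

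**The case against.** The best defence is that nobody would apply the numbers as printed. The column is organised by CTCAE grade, each row carries its grade, 7.6 ties grading to CTCAE v5.0, and two entries in the same table run the right way. Following the numbers would mean holding the drug in every eligible patient on day 1. Section 7.6.2 limits the table to events judged related to Tenalisib, and the platelet note leaves dose reduction to the investigator when the pre-treatment count is below 50. All of this stands, and it makes realistic harm small. It does not make the printed triggers right, and it does not settle Grade 3 neutropenia. One can argue that Table 3, as the specific dosing table, overrides the general precaution in 3.5.5, but the protocol does not say so.

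Three stronger readings are tempting, and the documents do not support them.

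- A reader might infer that non-febrile Grade 4 neutropenia is left with no instruction to stop. Section 3.5.5 covers it by grade.
- A reader might infer a conflict over restart. Section 7.6 says "Patients may resume Tenalisib, provided that the toxicity has resolved to Grade" 2 or lower, or baseline, whereas 7.6.1 uses ANC above 750/µL or baseline, and platelets above 50,000/µL. But 7.6.1 is written for delays beyond two weeks, and 7.6, 7.6.1 and the footnote to the neutropenia hold all bring the medical monitor into such delays. It reads as the specific rule for long delays with case-by-case review.
- A reader might infer that patients were misdosed. Nothing in the documents shows that.

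**Conclusion.** The point holds as a drafting error in a safety instruction. The leading inequality is reversed in four of four ranges, and in the text as read the second sign of the Grade 3 ANC row is reversed too. Taken literally, the printed ranges put no neutrophil or platelet count in the row meant for it. The finding rests on the leading signs being as printed. A reading fault is unlikely to explain the same reversal in all four rows when other comparisons in the table are correct. The claims that the Grade 3 ANC row is empty and that five signs are wrong rest on the one symbol discussed above.

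Practical weight is limited because the intended grades are plain. The Grade 3 neutropenia contradiction between 3.5.5 and Table 3 is a separate, smaller point that does not depend on any symbol.

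Neither point affects the analysis. SAP 10.6.2 summarises adverse events by CTCAE v5.0 grade, not by Table 3's numbers, and the notes under SAP 5.1 record that the study has closed. The value now is a correct record and safe reuse of the text.

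**What to change.** Print the Table 3 ranges as follows (×10⁹/L):

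- Grade 3 neutropenia: 0.5 ≤ ANC < 1.0
- Grade 4 neutropenia: ANC < 0.5
- Grade 3 thrombocytopenia: 25 ≤ PLT < 50
- Grade 4 thrombocytopenia: PLT < 25

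This changes five signs: two in the Grade 3 ANC row and one in each of the others (four in all if the PDF page shows ≥ in the Grade 3 ANC row).

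The sponsor should also state whether 3.5.5 (interrupt) or Table 3 (maintain) governs Grade 3 neutropenia. That needs a clinical decision and then one sentence in the section that gives way.

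No change to 7.6.1 is proposed. The cost is text only: no new assessments, and no change to the data collected or the analysis.
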